# **Study Population and Main Criteria for Inclusion/Exclusion:**

#### **Inclusion Criteria:**

Subjects must meet the following criteria to be included in the study:

- 1. Age ≥18 years of age; male or female.
- 2. HIV (confirmed by ELISA, western blot, OraQuick®, or viral loads) with histologically confirmed KS.
- 3. Willing to undergo serial tumor biopsies.
- 4. Capable of providing informed consent and complying with trial procedures.
- 5. KPS ≥70 (Appendix B)
- 6. Easter Cooperative Oncology Group (ECOG) PS 0-2.
- 7. Life expectancy ≥8 weeks.
- 8. Measurable (at accessible site or radiographic) tumor lesions according to ACTG TIS criteria (Appendix G).
- 9. Women must not be able to become pregnant (e.g. post-menopausal for at least 1 year, surgically sterile, or practicing adequate birth control methods) for the duration of the study. (Adequate contraception includes: oral contraception, implanted contraception, intrauterine device implanted for at least 3 months, or barrier method in conjunction with spermicide.)
- 10. Women of child bearing potential must have a negative serum or urine pregnancy test at the Screening Visit and be non-lactating.
- 11. Geographic accessibility to the site.

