# **Secondary Objectives:**

- 1. Evaluate the intratumoral kinetics of ALDOXORUBICIN and related biomarker expression through sequential biopsies of KS skin lesions.
- 2. Determine the change in performance status (PS) as measured by the Karnofsky Performance Status (KPS) (Appendix B).

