#### Tumor Pathology:

The following pathologic variables will be assessed over the course of the study:

- Concentration of drug within skin tumors and adjacent normal skin will be assessed using HPLC in the laboratory of [name] in the Louisiana Cancer Research Center.
- Routine histopathologic assessments and expression of KSHV-encoded LANA, secreted protein
  acidic and rich in cysteine (SPARC), gp60, and caveolin (which may relate to mechanisms of drug
  activity) within skin tumors will be assessed by [name] [name] in the Molecular and Histology
  Core Facility in the Louisiana Cancer Research Center. Expression will be assessed quantitatively
  using immunofluorescence analyses and fluorescence intensity quantification software.
  (Appendix F).

Name of Sponsor/Company: CytRx Corporation			
Protocol Number: ALDOXORUBICIN-P2-KS-01	Phase of Development: 2		

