### Secondary Objectives:

- Evaluate the intratumoral kinetics of ALDOXORUBICIN and related biomarker expression through sequential biopsies of KS skin lesions only on samples obtained at LSU Medical Center.
- 2. Determine the change in performance status (PS) as measured by the Karnofsky Performance Status (KPS) (Appendix B).
- 3. Determine the change in quality of life as measured by the KS Functional Assessment of HIV (FAHI) Quality of Life instrument (QoLI) (Appendix H).

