#### **Number of Subjects:**

Up to 20 subjects will be enrolled (10 in each arm) at 2-4 sites in the United States.

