# **Tumor Pathology:**

The following pathologic variables will be assessed over the course of the study only in subjects enrolled at the Louisiana State University (LSU) Health Science Center:

- Concentration of drug within skin tumors and adjacent normal skin will be assessed using HPLC in the laboratory of [name] in the Louisiana Cancer Research Center.
- Routine histopathologic assessments and expression of KSHV-encoded LANA, secreted protein
  acidic and rich in cysteine (SPARC), gp60, and caveolin (which may relate to mechanisms of drug
  activity) within skin tumors will be assessed by [name] [name] in the Molecular and Histology
  Core Facility in the Louisiana Cancer Research Center. Expression will be assessed quantitatively
  using immunofluorescence analyses and fluorescence intensity quantification software.
  (Appendix F).

Name of Sponsor/Company: CytRx Corporation				
Protocol Number: ALDOXORUBICIN-P2-KS-01	Phase of Development: 2			

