# **APPENDIX A: Schedule of Treatment and Evaluations**

	Screening -21 Days	Cycle 1	All Other Cycles	Cycle 2	Cycle 4	Every Odd Cycle	Every Fourth Cycle	End of Study or Early Termination	Follow- up 
Signed informed consent	Х								
Review inclusion/exclusion		Х							
Medical history 	Х								
Physical examination	X	Х	Х					X	
Height (cm)	Х								
Weight (kg)	Х	X	Х						
BSA calculation		X 	X 						
Vital signs 	Х	Х	Х					X	
KPS	Х	Х	Х					X	
FAHI QoL	Х						Х		
Tumor measurements 	X 				X8			X8	
ECG	Х	Χ				X		X 	
ECHO (with ejection fraction)	X				X 			X	
CBC w/differential & plts 	Х	X	Х					X	
Serum chemistries 	X*	Х	Х					X	
Urinalysis 	Х							X	
Serum/urine pregnancy test	Х								
ALDOXORUBICIN administration 		Х	Х						
Concomitant medications 	X	Х	Х					X	
Biopsy of tumor 	X			Х			X 		
AEs 	X	Х	Х					X	
Telephone follow-up 									Χ

NOTE: All assessments must be performed within 72 hours of each specified time parameter, except Cycle 1 (Section 5 for details).

\*Arterial blood gas test, if needed, to confirm acid levels.

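### Should the biopsy-willingness criterion be limited to LSU, now that only LSU samples are analysed?

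*Combined protocol and SAP*

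**What the plan says.** The file holds five successive versions of the synopsis and of the Appendix A schedule. The last one governs.

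- **Inclusion Criteria, no. 3:** "Willing to undergo serial tumor biopsies". The lead-in makes all criteria mandatory, and no site is exempted.
- **Number of Subjects:** "Up to 20 subjects will be enrolled (10 in each arm) at 2-4 sites in the United States".
- **Secondary Objectives, no. 1:** intratumoral kinetics and biomarker expression are evaluated "through sequential biopsies of KS skin lesions only on samples obtained at LSU Medical Center".
- **Tumor Pathology:** drug concentration, histopathology and marker expression are assessed "only in subjects enrolled at the Louisiana State University (LSU) Health Science Center".
- **Appendix A:** the row "Biopsy of tumor 13" (the number is a footnote mark) is ticked at screening, Cycle 2 and every fourth cycle. The text of footnote 13 is not in the public file.
- **Inclusion Criteria, no. 2:** entry at every site also needs HIV infection "with histologically confirmed KS", which is a separate diagnostic requirement.

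**The concern.** Serial biopsy willingness is a condition of entry everywhere, yet each stated use of the biopsies belongs to one site. The efficacy and safety variables need no biopsy, and the rationale mentions only the same drug-concentration and biomarker work. Histological confirmation of KS does not call for repeated sampling.

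Two things could be at stake. If subjects outside LSU are not biopsied, the criterion could exclude a willing and otherwise eligible candidate for refusing something that would never be asked of them, in a trial of only 20. If they are biopsied, they undergo invasive research sampling for which the public text describes no analysis. The first would be a needless restriction and the second a needless burden.

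**Working it through.** The documents give no figure to reproduce, so the check is a comparison of texts followed by a look at what each reading would change.

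**1. How the mismatch arose.** In the three single-site versions, all subjects were at LSU. The objective read "Evaluate the intratumoral kinetics of ALDOXORUBICIN and related biomarker expression through sequential biopsies of KS skin lesions" with no site limit, and the pathology section opened "The following pathologic variables will be assessed over the course of the study", also without one. Criterion 3, the objective and the pathology section covered the same people. When the trial moved to 2-4 sites, the LSU limit was written into the objective and the pathology section. The biopsy row was also rewritten, from every even cycle to screening, Cycle 2 and every fourth cycle. Criterion 3 kept its wording. An incomplete conforming edit is the natural explanation, although a deliberate common rule cannot be excluded.

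**2. Does the current text contradict itself?** The objective restricts which samples serve the kinetics analysis, and the pathology section restricts in whom the variables are assessed. Neither says that tissue is taken only at LSU. The schedule row shows no site limit in the cells. However, in the version that added the sites, footnote 13 was placed on the row label as well as in a cell, where it may qualify the whole row. The synopsis also presents only the main criteria, and the protocol body is not public. A willingness criterion for all sites beside a site-limited sub-study is untidy, but the two are not incompatible.

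**3. What each reading implies.**

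- *Biopsies at LSU only.* Criterion 3 is superfluous elsewhere. Its cost falls on candidates who are screened out. Its benefit is that all enrolled subjects passed the same entry rule.
- *Biopsies at every site.* Criterion 3 is needed everywhere. A version limited to LSU would admit subjects unwilling to have a scheduled procedure. The open question would then be the purpose of the samples, which the unseen text may answer.

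**4. Can the effect be sized?** A headcount outside LSU is 20 × (1 − LSU share), and the share is an assumption. Even enrolment gives 20 − 20/2 = 10 with two sites, 20 − 20/3 = 13.3 with three and 20 − 20/4 = 15 with four. An LSU share of 90% gives 20 × 0.10 = 2. None of these measures the harm. On the first reading, the people affected are not among the 20 enrolled. On the second, the count is only a ceiling, because enrolment is up to 20 and sampling outside LSU is not established. No refusal rate or biopsy count can be derived.

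**5. Effect on the analyses.** The criterion applies alike in both dose groups and at every site. The pathology analyses use LSU subjects, who must be willing under either wording. The primary objectives, preliminary efficacy and safety, do not use biopsy data. The sample size and all stated figures stay the same.

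**The case for a change.** The best argument for a change is that the mismatch lies within the current version and is cheap to remove. Criterion 4 already requires that subjects can comply with trial procedures, so criterion 3 adds something outside LSU only if biopsies are done there. If footnote 13 confines them to LSU, the criterion can only exclude. If it does not, invasive sampling lacks a stated analysis. On this view, some rewording is due whichever holds, and it adds no procedure.

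Part of this stands. The wording is out of line with the objective and the pathology section, and the public text offers no reason for keeping it at all sites. But the claim that it is wrong whichever holds goes too far: if footnote 13 or the protocol body gives a purpose for samples at other sites, a criterion for all sites is consistent.

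Nor is the rewording free. With the criterion limited to LSU, subjects there would be selected for biopsy willingness and the others would not. Site and willingness would be entangled with 10 subjects per arm, and site would have to be shown in the listings to make that visible. This exchanges a recruitment loss of unknown size for a possible difference between sites, also of unknown size.

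**Conclusion.** The inconsistency is probably a leftover from the move to several sites, and it does not call for a change to the plan. Followed as written, the criterion gives one eligibility rule across sites and dose groups, supports the LSU pathology work, and alters no primary objective, sample size or stated figure. The possible loss is a few candidates outside LSU who decline biopsies. The documents do not allow that number to be estimated, and narrowing the criterion would give up uniform entry to recover them.

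This rests on two assumptions: that sites read the criterion together with footnote 13 and the full protocol, and that those texts say where biopsies are taken and why. The public text does not show that subjects outside LSU undergo biopsies without a purpose. If the unseen text did show that, it would raise a question of patient burden, but still not one of statistical validity.

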#### Criteria for Evaluation:

### Efficacy:

- The following efficacy variables will be evaluated every even cycle:
  - 1. Tumor staging (ACTG TIS criteria [Appendix G])
  - 2. Number of skin lesions (if applicable)
  - 3. Size of individual skin lesions (if applicable)
  - 4. Nodularity of skin lesions (if applicable)
- Chest CT and abdominal MRI will be performed at baseline, prior to Cycle 4 and at end of treatment to evaluate visceral lesions.
- FAHI QoL Instrument at and every fourth cycle.

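### The only scheduled pregnancy test is at Screening, up to 21 days before dose 1; none is scheduled before any dose of an open-ended three-weekly regimen

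*Combined protocol and SAP*

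**What the plan says.** All references are to the latest of the five synopsis versions in the combined document.

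- **Inclusion Criteria, no. 9.** Women must be unable to become pregnant throughout the study. Contraception counts as a means of meeting this: the criterion accepts women "practicing adequate birth control methods) for the duration of the study".
- **Inclusion Criteria, no. 10.** "Women of child bearing potential must have a negative serum or urine pregnancy test at the Screening Visit and be non-lactating".
- **Appendix A.** The row "Serum/urine pregnancy test" has one mark, in the Screening column (window of 21 days). It has none at Cycle 1, at later cycles, at end of study or at follow-up, and it carries no footnote number. The row is the same in the four earlier versions.
- **Study Design and Methodology.** Dosing is on Day 1 and every 3 weeks after that, until progression, unacceptable toxicity or withdrawal of consent. No maximum number of cycles is given.
- **Number of Subjects.** Up to 20 in total. The number of women is not stated.

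**The concern.** The plan treats pregnancy as incompatible with treatment for the whole study, yet the visible schedule tests for it once, before the first dose. Criteria 9 and 10 do not conflict and Appendix A agrees with criterion 10, so this is a monitoring gap and not an inconsistency.

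If contraception fails, or if conception occurs too close to Screening for the test to show it, nothing on the schedule stops the next dose. Dosing would stop only when someone recognised the pregnancy clinically or found it by chance. The harm at stake is repeated exposure of a pregnancy to a cytotoxic drug. Efficacy and safety analyses are untouched.

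**Working it through.** **1. Age of the only result.** Taking Screening at its earliest, the test precedes dose *k* by 21 + 21(*k* − 1) days.

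- Dose 1: 21 days
- Cycle 4: 21 + 63 = 84 days
- Cycle 8: 21 + 147 = 168 days

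**2. Whether anything else on the schedule acts as a test.** Contraception is required throughout. Appendix A marks "Review inclusion/exclusion" at Cycle 1, but criterion 10 names the Screening Visit, so the Screening result satisfies that review. "Concomitant medications" are recorded every cycle and may show a contraceptive, not a pregnancy. Imaging is for another purpose: "Chest CT and abdominal MRI will be performed at baseline, prior to Cycle 4 and at end of treatment to evaluate visceral lesions". Its first repeat comes after three doses. Physical examination, weight and adverse events are also marked at every cycle. They could shorten the time to recognition, but none requires a pregnancy test.

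**3. Chance of a conception the Screening test misses.** The documents give no inputs for this, so I assume a contraceptive failure rate *r* of 1% to 20% per year and a lag *L* of 7 to 21 days from conception to a positive test. With *d* days from Screening to the dose:

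Risk = 1 − (1 − *r*)^((*d* + *L*)/365)

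| By | *d* (days) | *r* = 0.01, *L* = 7 | *r* = 0.20, *L* = 21 |
|---|---|---|---|
| Dose 1 | 21 | 0.077% | 2.535% |
| Cycle 4 | 84 | 0.250% | 6.218% |
| Cycle 8 | 168 | 0.481% | 10.912% |

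These are risks per woman at risk. They are illustrations, not bounds, and assume she stays on treatment to that cycle. For an assumed 1 to 5 such women, expected conceptions by Cycle 8 run from 1 × 0.00481 ≈ 0.005 to 5 × 0.10912 ≈ 0.55.

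**4. Doses given after a conception, through Cycle 8.** This does not depend on *r*. Doses fall on days 0, 21, …, 147 and the Screening test on day −21. Conception is uniform from day −21 − *L* to day 147. A test is positive from *L* days after conception, and dosing stops at a positive test or at clinical recognition *R* days after conception, whichever is first. Ranges of means are for *L* = 7 to 21.

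| Tests | Max, never recognised | Max, *R* = 84 | Max, *R* = 42 | Mean, *R* = 84 | Mean, *R* = 42 |
|---|---|---|---|---|---|
| Screening only (as planned) | 8 | 4 | 2 | 3.24–3.22 | 1.84–1.78 |
| Plus odd cycles | 2 | 2 | 2 | 0.80–1.33 | 0.80–1.33 |
| Plus every cycle | 1 | 1 | 1 | 0.32–0.89 | 0.32–0.89 |

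A single extra test at Cycle 1 leaves the never-recognised maximum at 8, because a conception within *L* days before that test is still missed. Most of the gain therefore comes from repeat tests.

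**The case against.** The strongest objection is that the operative text is not public. The note under Appendix A exempts Cycle 1 from the 72-hour window and points to Section 5. Neither that section nor the footnote texts (including those on serum chemistries) are available, so a repeat test may be required there. This stands as a limit on the claim. Nothing visible points to such a requirement, however: the pregnancy-test row has no footnote number, and the legible visit-monitoring lists name no pregnancy test.

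Second, the figure of 8 doses is extreme. It needs conception before dose 1 and no recognition through day 147, despite an examination every cycle and an abdominal MRI before Cycle 4. That is fair, and the recognised cases are the better guide. With recognition at 42 days the planned maximum is 2, no worse than with odd-cycle testing. The mean still falls, from 1.84 to 0.80 (*L* = 7) or from 1.78 to 1.33 (*L* = 21), and testing every cycle lowers the maximum to 1.

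Third, failure rate, lag, recognition time and number of women are all assumed. Expected conceptions span about 100-fold, and the Cycle 8 horizon ignores early stopping, which would lower the later figures. All of this stands; the absolute expected number is small. It does not change what happens to a woman who does conceive.

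Lastly, no supplied document sets a retest frequency, so the interval proposed here is a judgement.

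**Conclusion.** The concern holds for the latest synopsis and Appendix A. One pregnancy test is scheduled, at Screening, and no dose is preceded by a current one, although the requirement not to become pregnant runs for the whole study and dosing is open-ended.

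That finding, and the result ages in step 1, rest on the documents alone. The dose counts rest on the assumed recognition time and test lag: recognition at 42 to 84 days implies a mean of about 1.8 to 3.2 doses after a conception as planned, against 0.3 to 0.9 with a test before every dose. The chance that any conception occurs is small and poorly known.

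The plan should be changed because the potential harm is serious and the remedy is cheap. Confidence is medium, because Section 5 could already contain the requirement.

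**What to change.** For women of childbearing potential, mark the pregnancy-test row in Appendix A at Cycle 1 pre-dose and before each later dose; every odd cycle is the minimum. Add one sentence to criterion 10, or a footnote to the row, requiring a negative result before dosing. If Section 5 already requires this, show it in Appendix A.

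The sample can be urine, or the blood already taken for "Serum chemistries" at Cycle 1 and all other cycles, so no visit or invasive procedure is added. The cost is a small assay charge for few subjects and an occasional short dosing delay while a result is awaited. A pre-dose test cannot show a conception in the days just before it, so the change limits repeat dosing but cannot exclude one exposed dose.

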#### **Exclusion Criteria:**

Subjects meeting the following criteria will not be enrolled:

- 1. Prior exposure > 375 mg/m^2 of doxorubicin or pegylated liposomal doxorubicin (Doxil).
- 2. Surgery and/or radiation treatment < 4 weeks prior to Randomization.
- 3. Exposure to any investigational agent within 30 days of Randomization.
- 4. History of other malignancies (except cured basal cell carcinoma, superficial bladder cancer or carcinoma *in situ* of the cervix) unless documented free of cancer for ≥3 years.
- 5. Laboratory values: Screening serum creatinine >1.5 × upper limit of normal (ULN), alanine aminotransferase (ALT) > 2.5 × ULN, total bilirubin >1.5 × ULN, absolute neutrophil count (ANC) <1,500/mm³, platelet concentration <75,000/mm³, absolute lymphocyte count <1000/mm³, hematocrit level <25% for females or <27% for males, serum albumin ≤2.5 g/dL.
- 6. Anion gap > 16 meg/L or arterial blood pH <7.30.
- Evidence of central nervous system (CNS) hemorrhage National Cancer Institute Common Terminology Criteria for Adverse Events (NCI CTCAE) version 4.03 (Appendix C) grade 2 or greater on baseline MRI.
- 8. Clinically evident congestive heart failure (CHF) > class II of the New York Heart Association (NYHA) guidelines.
- 9. Current, serious, clinically significant cardiac arrhythmias, defined as the existence of an absolute arrhythmia or ventricular arrhythmias classified as Lown III, IV or V.
- 10. History or signs of active coronary artery disease with or without angina pectoris.
- 11. Serious myocardial dysfunction defined as ultrasound-determined absolute left ventricular ejection fraction (LVEF) <45% of predicted institutional normal value.
- 12. Active, clinically significant serious infection requiring treatment with antibacterial, antiviral (other than antiretroviral therapy), or antifungal therapy.
- 13. Major surgery within 4 weeks prior to Randomization.
- 14. Any condition that might interfere with the subject's participation in the study or in the evaluation of the study results.
- 15. Any condition that is unstable and could jeopardize the subject's participation in the study.

Name of Sponsor/Company: CytRx Corporation				
Protocol Number: ALDOXORUBICIN-P2-KS-01	Phase of Development: 2			

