#### **Exclusion Criteria:**

Subjects meeting the following criteria will not be enrolled:

- 1. Prior exposure to an anthracycline.
- 2. Surgery and/or radiation treatment < 4 weeks prior to Randomization.
- 3. Exposure to any investigational agent within 30 days of Randomization.
- 4. History of other malignancies (except cured basal cell carcinoma, superficial bladder cancer or carcinoma *in situ* of the cervix) unless documented free of cancer for ≥3 years.
- 5. Laboratory values: Screening serum creatinine >1.5 × upper limit of normal (ULN), alanine aminotransferase (ALT) > 2.5 × ULN, total bilirubin >1.5 × ULN, absolute neutrophil count (ANC) <1,500/mm³, platelet concentration <75,000/mm³, absolute lymphocyte count <1000/mm³, hematocrit level <25% for females or <27% for males, serum albumin ≤2.5 g/dL.
- 6. Evidence of central nervous system (CNS) hemorrhage National Cancer Institute Common Terminology Criteria for Adverse Events (NCI CTCAE) version 4.0 (published 28 May 2009) (Appendix C) grade 2 or greater on baseline MRI.
- Clinically evident congestive heart failure (CHF) > class II of the New York Heart Association (NYHA) guidelines.
- 8. Current, serious, clinically significant cardiac arrhythmias, defined as the existence of an absolute arrhythmia or ventricular arrhythmias classified as Lown III, IV or V.
- 9. History or signs of active coronary artery disease with or without angina pectoris.
- 10. Serious myocardial dysfunction defined as ultrasound-determined absolute left ventricular ejection fraction (LVEF) <45% of predicted institutional normal value.
- 11. Active, clinically significant serious infection requiring treatment with antibacterial, antiviral (other than antiretroviral therapy), or antifungal therapy.
- 12. Major surgery within 4 weeks prior to Randomization.
- 13. Any condition that might interfere with the subject's participation in the study or in the evaluation of the study results.
- 14. Any condition that is unstable and could jeopardize the subject's participation in the study.

Name of Sponsor/Company: CytRx Corporation			
Protocol Number: ALDOXORUBICIN-P2-KS-01	Phase of Development: 2		

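### Exclusion 11 calls the LVEF absolute but sets the limit at 45% of a normal value: read literally it does not exclude an LVEF of 35% (for any normal up to about 77.8%), while an absolute 45% limit would

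*Combined protocol and SAP*

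**What the plan says.** In the latest protocol synopsis (the one that adds the anion-gap exclusion), Exclusion Criteria no. 11 reads: "Serious myocardial dysfunction defined as ultrasound-determined absolute left ventricular ejection fraction (LVEF) <45% of predicted institutional normal value". The four preceding synopses carry the same sentence as no. 10, so it is neither a slip in one version nor an effect of reading the PDF.

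The other criteria in the same list that could bear on a low LVEF are:

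- No. 8: "Clinically evident congestive heart failure (CHF) > class II of the New York Heart Association (NYHA) guidelines".
- No. 9: "Current, serious, clinically significant cardiac arrhythmias", defined by type and Lown class.
- No. 10: "History or signs of active coronary artery disease with or without angina pectoris".
- Nos. 14 and 15, the catch-alls, which begin "Any condition that might interfere with the" and "Any condition that is unstable and could jeopardize the".

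None of these gives an LVEF figure.

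Two other parts of the plan matter here. Exclusion no. 1 has been relaxed over the protocol versions. It began as "Prior exposure to an anthracycline", then became more than 120 mg/m² of pegylated liposomal doxorubicin, and is now more than 375 mg/m² of doxorubicin or its pegylated liposomal form. Appendix A schedules an echocardiogram with ejection fraction at Screening.

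**The concern.** The sentence gives two incompatible instructions. LVEF is itself a percentage. An absolute LVEF below 45% is a complete rule and needs no reference value. A limit of 45% of a normal value is a different rule: it multiplies the normal by 0.45 and gives a much lower cut-off. A site following the closing phrase would admit patients whom a site following the word *absolute* would turn away.

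This is the only LVEF limit for entry in the supplied pages. According to Study Rationale and Significance, the drug works by releasing doxorubicin. The study design gives 75 or 110 mg/m² doxorubicin equivalents every 3 weeks until progression, unacceptable toxicity or withdrawal of consent. Three doses therefore add 3 × 75 = 225 to 3 × 110 = 330 mg/m² equivalents to whatever the patient has already had. When no prior anthracycline was allowed, a loose LVEF criterion had less to do. It now has to screen pretreated patients, and its wording has not changed. Echocardiogram findings also form part of the second primary objective. With 10 patients per arm, one patient entering with a markedly reduced LVEF is 10% of that arm's cardiac safety data.

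**Working it through.** **Inputs**

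- Limit: 45%, stated relative to the institution's predicted normal (Exclusion no. 11).
- Normal LVEF, *N*: not given in the supplied synopses or Appendix A. I assume 50–70% and show where the result does and does not depend on this.
- Example patient: LVEF 35%.

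The plan derives no figure on this point, so there is none to reproduce.

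**Rules under the two readings**

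- Relative (literal): exclude if LVEF < 0.45 × *N*.
- Absolute: exclude if LVEF < 45%.

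**When the readings agree.** Setting 0.45 × *N* = 45 gives *N* = 45 / 0.45 = 100. They coincide only for a normal LVEF of 100%.

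**Size of the difference**

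| Assumed normal *N* | Literal cut-off 0.45 × *N* | Points below an absolute 45% | LVEF 35%, literal | LVEF 35%, absolute |
|---|---|---|---|---|
| 50% | 22.5% | 22.5 | not excluded | excluded |
| 60% | 27.0% | 18.0 | not excluded | excluded |
| 70% | 31.5% | 13.5 | not excluded | excluded |

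**How far the example depends on *N*.** An LVEF of 35% escapes the literal rule as long as 0.45 × *N* is no more than 35, that is, *N* up to 35 / 0.45 = 77.8%. The example therefore holds across the whole assumed range and beyond it. At *N* = 80% the literal cut-off is 36.0%, and the patient would be excluded under both readings.

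**What relative limit would equal an absolute 45%.** For *N* = 70%, 45 / 70 = 64.3% of normal. For *N* = 50%, 45 / 50 = 90% of normal. The stated 45% is well short of either.

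**Whether another criterion closes the gap.** No. 8 needs heart failure that is clinically evident and above NYHA class II, so a patient with a low LVEF and few symptoms passes. Nos. 9 and 10 concern rhythm and coronary disease. Nos. 14 and 15 could be invoked for a low LVEF, but they depend on judgement and carry no number. Together they soften the gap without closing it.

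**The case against.** The strongest reply is that the text does not compel the relative reading. *Absolute* is also in the sentence, and an investigator may well take it as governing. If every site does so, no patient at 35% enters. The reference to serious dysfunction has been offered as a second cue for 45%, but it is weaker, since a lower cut-off fits that word at least as well. It is true that the documents do not show which limit was intended or how sites apply it. That does not rescue the wording: a safety threshold should not depend on which half of the sentence a site follows.

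Second, only the synopses and Appendix A are available. The protocol body may define the normal value, restate the limit or add another LVEF rule. A definition of the normal would fix the literal cut-off but could not bring it to 45% unless the normal were 100%. A restated or additional limit in the body would change the picture, so the finding is confined to the supplied pages, and the body should be checked before amending.

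Third, the inclusion criteria require KPS of at least 70 and ECOG 0–2, and Appendix A repeats the echocardiogram at Cycle 4 and at end of study. The performance-status criteria restrict symptomatic patients, and the later echocardiograms monitor patients already treated. Neither sets an entry LVEF.

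Fourth, the practical effect is unsized. Up to 20 patients are planned at 2–4 sites, and nothing in the documents says how many candidates would fall between the two cut-offs. That stands. High confidence applies to the conflict in the wording and to the arithmetic, not to a prediction that such patients will be enrolled.

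**Conclusion.** The concern holds. Taken literally, exclusion 11 sets the LVEF limit 13.5–22.5 points below 45% if the normal is 50–70%, a range I have assumed because the supplied pages give none. The 35% example is firmer, since it needs only a normal of no more than about 77.8%. The conclusion does not rest on knowing what the sponsor intended: a criterion whose literal application lets a markedly reduced LVEF past the only numerical cardiac-function limit in the supplied pages should be corrected. It should be fixed, but the discretionary exclusions and the unknown number of affected patients keep it from being graded more severely.

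**What to change.** Have the sponsor's safety lead confirm the intended limit, and check the protocol body for any other LVEF rule. Then make one of two changes to exclusion 11:

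- **Preferred, if 45% was meant as an LVEF:** delete everything after the 45%, so that the test is an ultrasound-determined absolute LVEF below 45%.
- **If a relative limit was intended:** state in the criterion the normal value to use and the LVEF cut-off that results. Sites then work from one number, and the safety lead can judge whether it is low enough to be a concern. Moving from this to an absolute 45% would tighten eligibility, which is why confirmation comes first.

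The cost is an amendment to one eligibility line. No new procedure is needed, because Appendix A already has the echocardiogram with ejection fraction at Screening. The downside is possibly a few more screen failures among patients with an LVEF between the literal cut-off and 45%. The documents give no basis for counting them.
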